## 5.2. ANALYSIS POPULATIONS

Enrolled subjects are all subjects who signed signed informed consent and completed screening.

All treated subjects (ie, Intent-to-Treat Safety [ITT-S] Population: subjects who receive any amount of study drug) will be included in the safety analyses.

Full Analysis Set Population (defined as subjects who have at least one post baseline efficacy assessment) will be included in the efficacy analyses.

All subjects with evaluable PK/PD profiles (ie, PK/PD Population) will be included in PK/PD analyses as appropriate.

#### 5.3. SUBJECT DISPOSITION

A summary table of subject disposition will be provided, to show the number of subjects screened, enrolled, and the number of subjects in the ITT-S population.

The number of subjects completing the study and withdrawing from the study will also be tabulated. Withdrawals will be categorized by primary reason for withdrawal.

# 5.4. PROTOCOL DEVIATIONS

Number of subjects with protocol deviations will be summarised for the following categories:

Document: \\SW20RND01\VistaTempDir\Temp28232\Shire\_0624\_209\_SAP\_v1 0.docx

Author: PPD Version Number: 1.0
Version Date: 21Jul2017

Template No: CS TP BS016 Revision 4 Reference: CS WI BS005

Effective Date: 01Apr2016

Copyright © 2009, 2010, 2012, 2016 Quintiles Transnational Corp. All rights reserved.

The contents of this document are confidential and proprietary to Quintiles Transnational Corp. Unauthorized use, disclosure or reproduction is strictly prohibited.

PROTOCOL: 0624 Page 13 of 35

- Procedures/tests
- Disallowed medications
- Inclusion/exclusion criteria
- Investigational product administration/study treatment
- Other

The date protocol deviations were identified together with the protocol deviation description will also be presented in a listing.

#### 5.5. **DEMOGRAPHIC AND OTHER BASELINE CHARACTERISTICS**

Demographics (age, age group of < 18, between 18 - 64,  $\ge 65$ , sex, ethnicity and race) will be summarized. In addition, the following baseline characteristics will be also be tabulated:

- Weight (kg) at screening
- Height (cm) at screening
- BMI (kg/m^2) at screening

In a separate table, summary of HAE history will also be tabulated for the following:

- Type of HAE
- Family history of HAE
- Time since last angioedema attack (days)
- Total number of angioedema attacks during 3 consecutive months prior to study drug administration
- Typical VAS score (mm) during 3 consecutive months prior to study drug administration
- Average overall duration (days) of angioedema attacks during 3 consecutive months prior to study drug administration, as collected in the Medical/Angioedema History electronic Case Report Form (eCRF)
- Average overall severity of angioedema attacks during 3 consecutive months prior to study drug administration, as collected in the Medical/Angioedema History eCRF
- Typical location(s) of angioedema attack during the 3 consecutive months prior to study drug administration

\\SW20RND01\\VistaTempDir\Temp28232\\Shire\_0624\_209\_SAP\_v1 0.docx Document:

Version Date: 21Jul2017

Version Number:

1.0

Reference: CS\_WI\_BS005

Template No: CS\_TP\_BS016 Revision 4

Effective Date: 01Apr2016

Author:

Shire
PROTOCOL: 0624-209
Page 14 of 35

Derivations will be constructed as follow:

# Body mass index (kg/m²)

... = 
$$\frac{h(1)}{h(1)^{100}}$$

presented to one decimal place.

#### Time since last angioedema attack (days)

time = first dose date - onset date of last angioedema attack prior to first dose

# **5.6.** EXTENT OF EXPOSURE

The average daily dose, total dose and duration of exposure will be summarized for study drug taken as 'Long-term prevention'.

Derivations will be constructed as follow:

#### **Duration of exposure (weeks)**

duration = (last dose date - first dose date + 1)/7

#### Total dose (U)

The sum of all study drug administered.

# Average daily dose (U/day)

$$average = \frac{()}{-} + 1()$$

#### 5.7. ANALYSIS OF EFFICACY

# 5.7.1. Prevention of Angioedema Attacks

An angioedema attack is defined as any subject-reported (or caregiver-reported) indication of swelling or pain at any location following a report of no swelling or pain on the previous day (ie, there must be a full symptom-free calendar day preceding the onset of symptoms for an attack to be considered a new attack). Therefore,

Attacks that progress from 1 site to another will be considered a single attack;

Document: \\SW20RND01\\VistaTempDir\Temp28232\\Shire\_0624\_209\_SAP\_v1 0.docx

Author: PPD Version Number: 1.0
Version Date: 21Jul2017

Template No: CS\_TP\_BS016 Revision 4 Reference: CS\_WI\_BS005

1.0

Reference: CS\_WI\_BS005

- Attacks that begin to regress and then worsen before complete resolution will be considered 1 attack; and
- Attacks that begin, appear to resolve, and then reappear without a symptom-free calendar day reported after the appearance of resolution will be considered 1 attack.

An angioedema attack does NOT include swelling due to trauma or arthritis, or symmetrical non-painful swelling of the lower extremities.

The following efficacy endpoints for prevention of angioedema attacks will be tabulated.

- The NNA during the treatment period, compared to the NNA for historical data for 3 months prior to study drug administration.
- Summary of all attacks during the treatment period, including:
  - Anatomic location. O
  - Severity (intensity). 0
  - Average duration of attacks.
  - Number of angioedema attacks treated with CINRYZE®, non-CINRYZE® C1-INH or not treated with C1-INH (including attacks treated with any medications other than C1-INH or untreated attacks).
- The number of subjects with pre- and post-treatment NNA values will also be presented for the following:
  - Number of subjects achieving >=50% reduction in NNA relative to NNA for Histotical data
  - Number of subjects achieving >=70% reduction in NNA relative to NNA for Histotical data
  - Number of subjects achieving >=90% reduction in NNA relative to NNA for Histotical data
- Effects of therapy on quality of life (results of AE-QoL questionnaire).

Derivations will be constructed as follow:

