4.1 Inclusion Criteria

To be eligible for this protocol, a subject must:

- 1. Be of Japanese descent, defined as born in Japan and having Japanese parents and Japanese maternal and paternal grandparents.
- 2. Be ≥ 2 years of age.
- 3. Meet the following minimum body weight criteria:
 - Subjects 2 to 5 years of age must weigh at least 12.5 kg; and
 - Subjects 6 years of age and above must weigh at least 25 kg.
- 4. Have a confirmed diagnosis of Type I or Type II HAE. **NOTE:** Diagnosis may be based on historical data including family history, clinical symptoms (characteristic attacks), and documentation of low level of C1 INH protein and/or C1 INH activity.
- 5. Have a history of at least one angioedema attack per month (on average) during the 3 consecutive months immediately before enrollment.
- 6. Agree to adhere to the protocol-defined schedule of assessments and procedures.
- 7. Agree to avoid his/her known angioedema attack triggers during the study to the best of his/her ability.
- 8. If a female of reproductive age, be postmenopausal (≥12 months following cessation of menstruation), surgically sterile, or following an acceptable method of birth control (and agree to continue its use through 1 month after the last dose of study drug):
 - Non-hormonal methods (eg, abstinence, barrier control) for at least 1 complete menstrual cycle before the Screening Visit.
 - Stable doses of estrogen and/or progestin containing products for at least 2 months before the Screening Visit.
- 9. If a male of reproductive age, be surgically sterile or agree to follow an acceptable method of birth control (eg, abstinence, barrier control) from the Screening Visit through 2 months after the last dose of study drug.
- 10. If an adult, be informed of the nature of the study and provide written informed consent before any study-specific procedures are performed.

OR

If a child or minor (<20 years of age), have a parent/legal guardian who is informed of the nature of the study provide written informed consent (ie, permission) for the child to

Protocol 0624-209 with Amendments 1, 2, 3, 4, and 5 CINRYZE (C1 inhibitor [human])

participate in the study before any study-specific procedures are performed. Assent will be obtained from children ≥14 years of age.

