5.2 Randomization

Subjects will not be randomized in this study.

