6.1 Medical History and Physical Examination

A medical history will be taken at the screening visit. All medical history findings that have been present/active within the 5 years before enrollment will be recorded in the CRF regardless of clinical relevance or presence at study start. Medical history findings that have not been present within the 5 years before enrollment will be recorded if deemed clinically relevant to the conduct of the study by the Investigator. The medical history should include any history of allergic reactions to drugs. In addition, the following information associated with the history of angioedema will be recorded in the CRF:

- HAE Type (I or II). If a subject does not have a confirmed diagnosis of HAE based on historical data, including C1 INH functional deficiency, the subject's diagnosis must be confirmed prior to treatment by C1 INH test results which demonstrate a quantitative and/or functional C1 INH deficiency; a blood sample may be collected at screening to determine a deficiency in the levels of C1 INH and/or C1 INH activity.
- Family history of HAE within first degree relatives (offspring, siblings, parents).
- If a central line has ever been used for administration of any medication, and if yes, is there currently a central line in place?
- Estimated onset date of last angioedema attack before enrollment (ie, prior to Day 1).

- Total number, typical locations, average overall duration (in days), and average overall severity of angioedema attacks experienced during the 3 consecutive months before the first dose.
- Visual Analogue Scale (VAS) typical score for the subject's angioedema attack pain during the 3 consecutive months before the first dose. Note: Subjects younger than 5 years of age do not need to complete the VAS.

The Investigator or designee will perform physical examinations at the time points specified in Schedule 1 and Schedule 3. Physical examinations will be performed in accordance with standard practices at the study site. Physical examination abnormalities observed at the screening visit will be recorded as medical history. New abnormalities or worsened pre-existing abnormalities observed post-screening should be recorded as AEs, as determined by the Investigator (see Section 9).

Body weight and height will be measured at the time points specified in Schedule 1 and Schedule 3.

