#### Number of angioedema attacks (per month)

The NNA during the treatment period is the number of angioedema attacks normalized for the number of days the subject participated in the period and multiplied by 30.4:

-	_	+1 30.4
presented to two decimal place.		
The NNA for historical data is the administration, divided by 3.	number of angioedema attack	s during 3 months prior to study drug
	h	
	3	

\\SW20RND01\VistaTempDir\Temp28232\Shire 0624 209 SAP v1 0.docx Document: Version Number:

Author: Version Date: 21Jul2017

Template No: CS\_TP\_BS016 Revision 4

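### Entry and the NNA baseline rest on nearly the same 3-month attack count, so regression to the mean favours CINRYZE by an amount that depends on a true attack rate the documents do not give

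*SAP*

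**What the plan says.** **Entry.** Protocol 4.1, criterion 5, requires a history of at least one "angioedema attack per month (on average) during the 3 consecutive months immediately before enrollment", that is, a count of 3 or more.

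**Baseline.** Protocol 6.1 records the total number of "angioedema attacks experienced during the 3 consecutive months before the first dose". SAP 5.5 lists the same item: "Total number of angioedema attacks during 3 consecutive months prior to study drug administration". In the SAP derivation the historical NNA is this count taken before study drug "administration, divided by 3". The on-treatment NNA is the attack count "normalized for the number of days the subject participated in the period and multiplied by 30.4".

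**Comparison.** SAP 5.7.1 sets the two NNA values against each other: "The NNA during the treatment period, compared to the NNA for historical data for 3 months prior to study drug administration". It also defines responders from the historical value, for example "Number of subjects achieving >=50% reduction in NNA relative to NNA for Histotical data", with the same at 70% and 90%.

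**Control.** Protocol 5.2: "Subjects will not be randomized in this study". The study is single-arm and open-label, with no run-in.

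**Safeguards.** The two NNA sensitivity analyses in SAP 5.7.4 concern dosing compliance only. Neither document mentions regression to the mean or gives an expected attack rate for the enrolled population.

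**The concern.** When subjects are admitted because a variable count reached a floor, those whose count was high by chance get in and those whose count was low by chance do not. The admitted group's historical mean therefore exceeds its true mean. A later count falls back towards the true mean even if the drug does nothing, and the plan would credit that fall to CINRYZE.

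The historical contrast is the study's only internal comparison of attack rates for prevention, and the Protocol rationale (1.2) says the study is meant to confirm efficacy in Japanese patients. The tables give no figure for what an inert drug would produce, so a reader cannot tell how much of a fall, or how many responders, to discount.

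**Working it through.** The documents state no expected fall or responder rate, so there is no planned figure to reproduce. The check asks what the planned table would show for a drug with no effect.

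**Inputs from the documents**
- Entry floor: 3 attacks in 3 months (Protocol 4.1).
- Historical NNA = count / 3; on-treatment NNA = count / days × 30.4 (SAP derivation).
- Screening at most 21 days before first dose, possibly the same day (Protocol 3 and Schedule 1). The entry and baseline windows therefore coincide or share about 70 of 91 days.
- Overseas placebo rate of 12.8 per 12 weeks (Protocol 1.1.2): 12.8 / 84 × 30.4 = 4.63 per month. It is the only untreated rate in the documents.

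**Assumptions**
- Attacks are Poisson with true rate m per month, unchanged on treatment.
- There are 24 doses at an average spacing of 3.5 days, so 23 × 3.5 + 1 = 81.5 days. The fall in NNA does not depend on this length; the responder rates do, slightly.

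**Fall in NNA, identical windows, one common rate.** Let X be Poisson with mean 3m. Selection on X ≥ 3 gives a mean historical NNA of m × P(X ≥ 2) / P(X ≥ 3). The apparent fall is therefore 1 − P(X ≥ 3) / P(X ≥ 2).
- m = 1.0: 1 − 0.577/0.801 = 28% (historical 1.39, on treatment 1.00).
- m = 1.5: 1 − 0.826/0.939 = 12% (1.70 against 1.50).
- m = 2: 1 − 0.938/0.983 = 4.5% (2.10 against 2.00).
- m = 4.63: about 0%.
- m = 0.5: 57% (1.16 against 0.50).

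**Subjects meeting the 50% criterion under no effect.** A subject responds if on-treatment NNA ≤ 0.5 × historical NNA. For comparison, the selection-free case takes any subject with at least one historical attack.

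| True rate per month | With entry floor | Without | Added by selection | Expected of 6 (with floor) |
|---|---|---|---|---|
| 1.0 | 34.5% | 23.6% | 10.9 points | 2.1 |
| 1.5 | 22.2% | 18.8% | 3.4 points | 1.3 |
| 2 | 16.3% | 15.3% | 1.0 point | 1.0 |
| 4.63 | 5.0% | 5.0% | 0 | 0.3 |

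With 84 days instead of 81.5, the first column becomes 33%, 21%, 15% and 5%. At the 90% threshold, selection adds nothing. At these rates that criterion in practice requires zero on-treatment attacks, whatever the historical count. The proportions are about 7%, 2% and 0.5% at 1.0, 1.5 and 2 per month, with or without the floor.

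**Screening lag of 21 days.** Only 70.2 of the 91.2 baseline days were selected on. At m = 1.0 the mean baseline count is 4.165 × 70.2/91.2 + 21/30.4 = 3.90. The historical NNA is then 1.30 and the fall 23%. At m = 1.5 the fall is 9.5%.

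**Between-subject variation.** With gamma-distributed rates (CV 0.6 to 1.0), the falls are 19% to 12.5% at a population mean of 1.0 per month, 10% to 7% at 1.5, 6% to 5% at 2, and about 1% at 4.63.

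**Does a correction work?** Given a subject's total, the historical count is binomial with probability 91.2 / (91.2 + ρ × days), where ρ is the rate ratio. Conditioning also on a historical count of at least 3 removes the selection. In simulated trials of 6 subjects (gamma CV 0.6, identical windows):
- True ratio 1: the uncorrected pooled ratio had median 0.80 (mean 1.0 per month) and 0.90 (1.5 per month); the truncated estimate had 1.01 and 1.00.
- True ratio 0.5 at 1.5 per month: 0.45 uncorrected and 0.51 truncated.

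**The case against.** The strongest reply is that no single size can be given to the bias. The documents give no attack rate for this population, and Protocol section 1 says frequency varies widely between patients, which makes the bias smaller at mean rates of 1.0 to 1.5. At the overseas placebo rate it vanishes. This stands. A reader might infer from the 1.0 and 1.5 cases that an inert drug would always show a fall of 12 to 28%; the documents do not support that. Nor does the overseas rate show that the bias is negligible here, because that population may differ and the entry floor in this trial is only one attack per month.

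A reader might also infer that half of the subjects would respond to an inert drug, or that every null responder is a selection artefact. Neither follows. Half responding needs a true rate near 0.5 per month with little variation between subjects. At 1.0 per month and above, most null responders come from chance in small counts. Of 6 subjects, selection adds about 0.65, 0.2 and 0.06 responders at 1.0, 1.5 and 2 per month.

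The analysis is descriptive, with no test or decision rule, so no type I error is at stake. That lowers the severity, but the estimate remains biased and is shown without a reference. Protocol 7.3 allows results to be superimposed on overseas data, but that is optional and external, and does not correct the contrast.

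**Conclusion.** The concern holds as a bias of known direction and unknown size. The entry count and the baseline count are nearly the same variable, there is no control arm, and nothing in the plan allows for the selection. Under a common Poisson rate and identical windows, the fall in NNA from an inert drug runs from about 28% at 1.0 per month to about 0% at 4.6, and is larger below 1.0. A screening lag makes it smaller, as does variation between subjects at mean rates of 1.0 to 1.5. The responder table needs a null reference mainly because small counts vary by chance, and secondarily because of selection. The consequence is for interpretation of the NNA change and the 50% and 70% responder counts. Severity: should-fix.

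**What to change.** 1. Keep the SAP 5.7.1 NNA table as the descriptive display.
2. Add to SAP 5.7.4 a sensitivity analysis reporting the within-subject rate ratio with a 95% CI, from the conditional binomial likelihood of historical and on-treatment counts, with days as offsets and the historical count left-truncated at 3.
3. Beside the 50, 70 and 90% responder counts, print the numbers expected at a rate ratio of 1 over a stated range of true rates. This covers both chance and selection.
4. State in the report that the historical contrast includes regression to the mean.

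**Cost.** SAP wording and one small program, using counts and days already collected. The reduction may look less favourable. The interval will be wide with 6 subjects: in simulation at a true ratio of 0.5 and a mean of 1.0 per month, the median 95% interval was 0.22 to 1.07. A subject with exactly 3 historical and 0 on-treatment attacks contributes nothing to the truncated estimate, because that split is certain given a total of 3. Truncating the first-dose count at 3 is only approximate when screening precedes dosing. Bias from drift in a subject's own rate remains. For these reasons the truncated estimate belongs beside the planned table and should not replace it.

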#### 5.7.4. SENSITIVITY ANALYSIS

The following sensitivity analyses will be performed for efficacy analysis on NNA described in Section 5.7.1.

The first sensitivity analysis includes only subjects with treatment compliance. The definition of treatment compliance will be given in Section 5.8.8. That is, only subjects who have no dose interruption and receive 24 complete infusions are included in the analysis.

In the second sensitivity analysis, all FAS subjects will be included in this sensitivity analysis, however data will only include up to the point when non-treatment compliance occurred.

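### The 50/70/90% responder counts set no minimum time on treatment, so a subject who stops early without an attack counts as a responder at every threshold

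*SAP*

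**What the plan says.** SAP 5.7.1 introduces the responder counts with "The number of subjects with pre- and post-treatment NNA values will also be presented for the following" and lists reductions of at least 50, 70 and 90%, the last being "Number of subjects achieving >=90% reduction in NNA relative to NNA for Histotical data". Having both NNA values is the only condition stated.

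The derivation in the same section makes on-treatment NNA the attack count "normalized for the number of days the subject participated in the period and multiplied by 30.4". Historical NNA is the count over the 3 months before study drug "administration, divided by 3". Neither has a minimum observation time.

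SAP 5.2 defines the efficacy population as subjects "defined as subjects who have at least one post baseline efficacy assessment". The daily diary starts at Dosing Visit 1 (protocol 6.11), so a few days on study are probably enough to enter it. SAP 7.1 imputes only missing adverse event severity and causality, so no rule makes an early stopper a non-responder.

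SAP 5.7.4 plans two sensitivity analyses on NNA. The first keeps only subjects with 24 complete infusions and no dose interruption. The second keeps the whole Full Analysis Set, but "data will only include up to the point when non-treatment compliance occurred". In Appendix I both appear as attack-summary tables (14.2.1.2.1 and 14.2.1.2.2). Responder Table 14.2.1.3 is listed once, on the Full Analysis Set.

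**The concern.** Attacks are discrete and, at the lower end of the eligible range, infrequent. A short observation can be attack-free by chance, and zero attacks is a 100% reduction whatever the number of days. The same scaling works the other way: a single attack in a few days becomes a high monthly rate.

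The documents foresee early stopping. Protocol 5.5.1 discontinues study drug after an anaphylactic reaction. Protocol 5.5.2 interrupts it after a thrombotic event, which can lead to discontinuation. Protocol 6.15.1 lists adverse event and lack of efficacy among the reasons for withdrawal. Protocol 6.15 allows extra subjects to be enrolled so that at least 6 complete, but nothing removes a treated subject who stopped from the Full Analysis Set. As written, a subject withdrawn for anaphylaxis after one or two doses, with diary data and no attack, would be tabulated as a 90% responder.

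The study is uncontrolled and may have only 6 or 7 subjects, so one classification is visible in the reported percentage.

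**Working it through.** The plan gives no figure to reproduce: the study is descriptive, with no power calculation or success criterion. The check applies the SAP's own derivation.

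**Inputs from the documents**
- On-treatment NNA = attacks / days × 30.4; historical NNA = 3-month count / 3 (SAP 5.7.1).
- Lowest eligible rate: 1 attack per month on average (protocol 4.1).
- Overseas placebo rate: 12.8 attacks per 12 weeks (protocol 1.1.2), so 12.8 / 84 × 30.4 = 4.63/month.
- Planned treatment period: 12 weeks = 84 days; at least 6 completers.

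**Assumptions not in the documents**
- Attacks are Poisson at the unchanged historical rate (no drug effect).
- Illustrative rate of 2/month; stopping at day 7.

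**Step 1: what the rule does.** Reduction = 1 − (on-treatment NNA / historical NNA). With zero attacks this is 100% for any number of days, without any model. One attack in 7 days gives 30.4 / 7 = 4.34/month. At a historical 4.63/month that is a reduction of 1 − 4.34/4.63 = 6%; at 1 or 2/month it is an increase. The subject fails all three thresholds.

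**Step 2: chance of being a 90% responder with no drug effect.** At 7 days, only zero attacks qualifies at these rates, so P = exp(−rate × 7 / 30.4). At 84 days, up to 10% of the expected count is allowed: zero attacks at 1 and 2/month, and at most one at 4.63/month (10% of 12.8 is 1.28).

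| Historical rate | 7 days | 84 days |
|---|---|---|
| 1/month | exp(−0.230) = 0.794 | exp(−2.763) = 0.063 |
| 2/month | exp(−0.461) = 0.631 | exp(−5.526) = 0.004 |
| 4.63/month | exp(−1.067) = 0.344 | exp(−12.8) × (1 + 12.8) < 0.001 |

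With clustered attacks (negative binomial, size 1), the direction holds. Day 7 against day 84 is 0.813 against 0.266 at 1/month, and 0.685 against 0.153 at 2/month.

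**Step 3: effect on the table.** Take 6 completers, k of them responders, plus one attack-free early stopper.
- Responder against non-responder for that one subject: 1/7 = 14.3 points.
- Shift from the completer rate as the SAP is written: (k+1)/7 − k/6 = (6−k)/42. This is +14.3 points at k = 0, +2.4 at k = 5 and 0 at k = 6.
- Shift if that subject is counted as a non-responder: k/7 − k/6 = −k/42. At k = 5 this is −11.9 points (83.3% to 71.4%).

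**Step 4: expected 90% share with no drug effect, 6 completers plus one subject stopping at day 7.**
- 1/month: (6 × 0.063 + 0.794) / 7 = 16.8% as written; 6 × 0.063 / 7 = 5.4% with the stopper as a non-responder.
- 2/month: 9.4% against 0.3%.

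**The case against.** The strongest reply is that the problem may never arise. It needs a treated subject who stops early, and the documents give neither a dropout rate nor a count of discontinuations. That stands, and it limits the weight of the point.

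A reader might infer that any short observation is usually attack-free. The documents do not support that in general. The 79% figure uses the entry minimum; at the overseas placebo rate an attack-free week has a chance of about 34%. That population may differ from this one, so the range should be shown. Nor is the distortion always favourable, since an early stopper with one attack fails every threshold at the rates considered. A subject leaving for lack of efficacy would probably have had attacks.

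A reader might also take 14 points as the inflation of the reported rate. It is the swing for one subject between responder and non-responder. The shift from the completer rate is (6−k)/42, which is small when most completers respond.

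Section 5.7.4 refers to the efficacy analysis on NNA, and the responder counts are built on NNA, so it could be read to cover them. But no such output is listed. The first analysis drops non-compliant subjects and does not count them as failures. The second cuts follow-up and can create further short-period NNAs.

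Median and range accompany the mean (SAP 5.1), and terminations, exposure, compliance and attacks are listed by subject. A careful reader could find a short-exposure responder, but the responder table would not show it.

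Finally, counting every non-completer as a failure has its own bias. With one non-completer it moves the rate further from the completer rate than the present rule whenever k exceeds 3. That stands, and it argues against making it the only row.

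**Conclusion.** The point holds. SAP 5.7.1 sets no minimum exposure for the responder counts, and an attack-free early stopper scores a 100% reduction by arithmetic. The probabilities in the working rest on Poisson attacks at an unchanged historical rate and an assumed stop at day 7. The practical effect depends on whether any treated subject stops early, which the documents do not say.

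A reader might conclude that the study's main prevention result is biased in favour of the drug. The documents do not support that. Responder thresholds are absent from protocol 7.6.1, the SAP presents them as an addition to the comparison of NNA with historical data, and there is no test or success criterion to affect. The defect is an unstable classification over short follow-up in a very small descriptive table. It is worth repairing because the repair is cheap.

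**What to change.** In SAP 5.7.1 and Table 14.2.1.3, report two rows side by side at each threshold:

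- (a) responders by observed-days NNA, as now;
- (b) the same, with Full Analysis Set subjects who do not complete the treatment period counted as non-responders.

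Define completion in advance, for example by the study-completion status in the disposition table. The definition matters because protocol 5.5.2 allows dosing to be interrupted and resumed, so 84 days, 24 doses and study completion need not coincide.

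Show days observed for each non-completer. Beside mean NNA in Table 14.2.1.1 and both sensitivity tables, add the pooled rate (total attacks / total days × 30.4), so that each subject counts in proportion to the time observed.

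The cost is SAP wording and a few table rows, with no new data. If every subject completes, rows (a) and (b) agree. The downside is that row (b) is conservative and can be noticeably below the completer rate (5/7 = 71.4% against 5/6 = 83.3%), because a subject who stops late while attack-free counts there as a failure. Row (a) keeps that subject visible.
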